11.14 Time since MS onset/diagnosis

Time in years since MS onset is calculated from date of informed consent – MS onset date / 365.25 days if the category of medical history is 'History of MS'.

Time in years since MS diagnosis is calculated from date of inform consent – MS Diagnosis date / 365.25 days.

11.15 Body Mass Index (kg/m²) at study Baseline

Is calculated as:

Body Mass Index (BMI) [kg/m²] =
$$\frac{weight [kg]at \ baseline}{height [cm]^2 \ at \ screening} \times 10000$$

11.16 Software

All analyses will be performed using SAS® Software version 9.4 or higher.

12 Trial Subjects

The subsections in this section include specifications for reporting participant disposition and treatment/trial discontinuations.

12.1 Disposition of Subjects and Discontinuations

A table on screened participants describing the number and percent of participants in each of following disposition categories will be produced by treatment group:

- Total number of screened subjects, i.e. subjects that gave informed consent (overall summary only)
- Number of subjects who discontinued prior to randomization and reason (overall summary only)
- Number of randomized subjects
- Number of randomized subjects who did not start treatment
- Number of randomized subjects who completed the first 24 weeks of treatment
- Number of randomized subjects who permanently discontinued treatment prior to Week 24 and reason
- Number of randomized subjects who permanently discontinued treatment after Week 24 and prior to OLE and reason
- Number of randomized subjects who completed 48 weeks of treatment
 - Number of randomized subjects who signed the OLE Informed Consent
 - Number of randomized subjects who did not sign it
- Number of randomized subjects who entered OLE at dose 75 mg QD and switched to 75 mg BID during the OLE

- Number of subjects who discontinued treatment after OLE Week 0 and prior to OLE Week 48
- Number of subjects still on treatment at OLE Week 48
- Number of subjects who discontinued treatment after OLE Week 48 and prior to OLE Week 96
- Number of subjects who completed the OLE treatment at OLE Week 96
- Number of subjects who entered a gap period at OLE Week 96
- Number of subjects still on treatment at OLE Week 96
- Number of subjects who discontinued treatment after OLE Week 96 and prior to OLE Week 144
- Number of subjects still on treatment at OLE Week 144
- Number of subjects who discontinued treatment after OLE Week 144 and prior to OLE Week
 192
- Number of subjects still on treatment at OLE Week 192
- Number of subjects who discontinued treatment after OLE Week 192 and prior to OLE Week 240
- Number of subjects still on treatment at OLE Week 240
- Number of subjects who discontinued treatment after OLE Week 240 and prior to OLE Week 288
- Number of subjects still on treatment at OLE Week 288
- Number of subjects who discontinued treatment after OLE Week 288 and prior to OLE Week 336
- Number of subjects still on treatment at OLE Week 336
- Number of subjects who completed treatment during OLE. A participant is considered to have completed the OLE if he/she completed the End of Treatment Visit for the OLE Period and was assigned the status 'Completed', or if the main reason for treatment discontinuation was "Other, specify: Study terminated by Sponsor".
- Number of randomized subjects who permanently discontinued treatment during OLE and reason. COVID-19 related reason for discontinuation will be reported separately from the "Other" reason.
- Number of randomized subjects in the follow-up phase who have not completed the trial (ie, treatment completed or discontinued without documented Safety Follow-up/End of Trial Visit)
- Number of randomized subjects who completed the trial
 - Number of randomized subjects who completed the trial at Week 52
 - Number of randomized subjects who completed the trial at OLE Week 100
 - Number of randomized subjects who completed the trial at OLE Week 340
 - Number of randomized subjects who completed the trial at end of trial

- Number of randomized subjects who discontinued from trial after randomization and prior to OLE and reason.
- Number of randomized subjects who discontinued from trial during OLE overall, and by year of OLE (on or before OLE W48, OLE W48 OLE W96 etc.) and reason. COVID-19 related reason for discontinuation will be reported separately from the "Other" reason.

A table based on screened subjects describing the number and percent of subjects in each analysis set by treatment groups will be produced:

- Number of screened subjects
- Number of subjects included in the SAF
- Number of subjects included in the SAF-OLE
- Number of subjects included in the SAF-SWOLE
- Number of subjects included in the mITT
- Number of subjects included in the mITT-OLE

A table describing the number of participants by region, country within region and site will be produced by analysis set. A listing with participants by analysis set will be provided.

Study and treatment discontinuation/completion status will be listed for all participants in the SAF-OLE analysis set. The details of who discontinued/completed treatment or study will be provided with their reason for discontinuation (if applicable) as well as, treatment group, subject ID, First Date (relative day)/ Last Date (relative day) of dosing, first date of dosing in OLE, date of the switch during OLE (if switch performed), treatment and study discontinuation dates (relative day).

Participants with study participation impacted by the Ukraine crisis will also be listed with a description of the different events and impacts. This could include study intervention discontinuation, study discontinuation, protocol deviations, missed doses and missed visits.

12.2 Protocol Deviations

12.2.1 Important Protocol Deviations

The following summary tables and listings of important protocol deviations (IPDs) during the DBP and the OLE period will be provided:

- Table providing frequency of subjects with at least one IPD and frequency for each type of IPD; Ukraine crisis related IPDs will also be summarized as a separate category within the table.
- Table providing frequency for each type of minor Ukraine crisis related PDev.
- Listing of important protocol deviations
- A specific listing for Ukraine crisis related IPDs/PDevs.

Ukraine crisis related PDevs will include all PDevs including the mention "BCP22" or "BCP" within their description.

12.2.2 Reasons Leading to the Exclusion from an Analysis Set

Not applicable.

13 Demographics and Other Baseline Characteristics

Demographics, baseline disease characteristics, and other baseline characteristics at study baseline will be summarized based on the SAF-OLE analysis set, presented by treatment group plus combined across treatment groups (i.e. "Total").

Supportive listings will be based on the SAF-OLE analysis set, with subjects flagged according to membership in the SAF-SWOLE analysis sets.

13.1 Demographics

- Demographic characteristics
 - · Sex: male, female
 - Race: White, Black or African American, Asian, American Indian or Alaska Native, Native Hawaiian or Other Pacific Islander, Other
 - Ethnicity: Hispanic or Latino, Not Hispanic or Latino
 - Age (years) at informed consent: summary statistics
- Pooled Region (US or Western Europe, Eastern Europe, Rest of the World)
- Geographic/Capability Region (US, Western Europe, Eastern Europe and CCl Rest of the World)
- European Economic Area (EEA)
- A listing with actual treatment group, subject ID, analysis set, age, sex, race, ethnicity, height, weight, BMI, country and region will also be presented.

Specifications for computation:

- Age (years):
 - (date of given informed consent date of birth + 1) / 365.25
 - In case of missing day for at least one date, but month and year available for both dates, the
 day of informed consent and the day of birth will be set to 1 and the formula above will be
 used.
 - In case of missing month for at least one date, but year available for both dates, the month
 of informed consent and the day and month of birth will be set to 1 and the formula above
 will be used.
- Site codes will be used for the determination of the participants geographic region.

13.2 Medical History

Relevant past and present medical conditions at study baseline will be summarized from the "Medical History Details" eCRF page.

For this analysis, the Medical Dictionary for Regulatory Activities (MedDRA), current version, PT as event category and MedDRA SOC body term as Body System category will be used. The MedDRA version used will be indicated in a footnote. Medical history will be tabulated by SOC and PT. SOC and PT will be alphabetically sorted. Medical history will be also listed.

13.3 Other Baseline Characteristics

13.3.1 Disease history

Information on MS baseline disease characteristics, based on data collected at study baseline will be summarized in total and by treatment group for participants enrolled in the OLE and they will also be listed.

Descriptive statistics will be presented for:

- Type of MS, either relapsing-remitting MS or secondary progressive MS
- Time (years) since MS onset (first symptom)
- Time (years) since MS diagnosis
- Major systems affected
- Number of relapses in the year prior to randomization
- Number of relapses in the last 2 years before screening
- EDSS score
- Scores for each of the 7 Functional Systems (Visual, Brainstem, Pyramidal, Cerebellar, Sensory, Bowel/Bladder, Cerebral) and score for Ambulation used to derive EDSS score.
- Presence of at least 1 T1 Gd+ lesion within 6 months prior to randomization
- Number of T1 Gd+ lesions
- Volume of T1 Gd+ lesions
- Volume of T2 lesions

For time since MS onset or MS diagnosis, a missing onset day/month will be replaced by 1 for duration derivation.

13.3.2 Other

Descriptive statistics will be presented for physical examination as continuous variables: Height (cm), Weight (kg) and BMI (kg/m²).

Analyses of baseline characteristics with respect to ECGs and clinical laboratory evaluations are discussed in Section 17 Safety.

14 Previous or Concomitant Medications/Procedures

Medications/procedures will be presented on the SAF-OLE Analysis Set.

Concomitant medications are medications, other than IMPs, which are taken by participants any time on-trial (on or after the first day of IMP treatment for each participant). Concomitant medications include those started prior to and continued during administration of IMP, as well as those that were started after first administration of IMP. If the date values do not allow a medication to be classified as a non-concomitant medication, the medication will be considered as a concomitant medication.

Concomitant medications during OLE treatment period are defined as medications starting on or after the first IMP administration during OLE period or starting before first administration during OLE but ending or ongoing after first administration during OLE period.

Previous medications are medications, other than trial medications, which started before first administration of IMP during the DBP. Previous medications include those that were continued during administration of IMP during the DBP, as well as those discontinued prior to first administration of IMP during the DBP. If the date values do not allow a medication to be classified as concomitant medication, the medication will be considered as a previous medication.

Concurrent procedures are procedures which were undertaken any time on trial. If the date values do not allow a procedure to be classified as a non-concomitant procedure, the procedure will be considered as a concomitant procedure.

Concurrent procedures during OLE treatment period are defined as procedures starting on or after the first IMP administration during OLE period or starting before first administration during OLE but ending or ongoing after first administration during the OLE period.

Concomitant medications and concurrent procedures occurring during the OLE period will be tabulated.

For concomitant medication during the OLE the ATC-second level and preferred term will be tabulated as given from the World Health Organization Drug Dictionary (WHO-DD) current version. In case multiple ATCs are assigned to a drug, all ATC-2nd level terms will be used for reporting.

Concurrent procedures during the OLE period will be classified by medical review. Number of participants with concomitant procedures (starting prior to first dose of trial treatment, on or after the first day of IMP and prior to first dose during the OLE period and starting after first dose during the OLE period) and by type of procedure (as classified by medical review) will be summarized by treatment group and listed.

Listings of concomitant medications and concomitant procedures during the OLE will be provided.

Disease Modifying Therapy (DMT) is not captured in the eCRF but is of interest for the analysis. In order to identify DMTs, the list of all previous medications was reviewed by the Merck medical team and the flag for DMT was assigned retrospectively (refer to Appendix 19.7 for list of identified DMTs). Flags were then created from this list in ADaM:

- Prior DMTs from Prior Medications eCRF (see definition for previous medication in section above),
- subjects with at least one prior DMT,
- subjects with more than one prior DMT,
- number of prior DMTs per subject.

Tables for Prior DMT will be created based on the SAF and SAF-OLE analysis sets with selection on the previous medications and presenting number of subjects with at least one prior DMT, number of subjects with more than one prior DMT and number of subjects per prior DMT (WHO-DD preferred term).

15 Treatment Compliance and Exposure

Exposure and compliance will be presented on the SAF-OLE and SAF-SWOLE Analysis Sets.

Planned administration of Evobrutinib during OLE

Each kit contains 24 tablets of 25 mg of Evobrutinib which is enough medication for the administration of 3 tablets per day (so 75 mg in total) for 8 days. On OLE Day 1, participants not treated with Tecfidera during the DBP received 12 kits. From OLE Week 12 until OLE Week 84, these participants received between 11 and 13 kits depending on the quantity of kits carried over from last visit. On OLE Day 1, participants treated with Tecfidera during the DBP received 5 kits. From OLE Week 4 until OLE Week 8, they received between 4 and 6 kits depending on the quantity of kits carried over from last visit. At each trial visit from OLE Week 12, participants were given treatment kits containing the number of tablets needed up to the next planned trial visit depending on the kits carried over from last visit. Participants received 75 mg of Evobrutinib QD (once a day) until they switched to the dose of 75 mg of Evobrutinib BID.

Once a participant switched to the new dose of 75 mg BID and new kits were available, each kit contained 48 tablets of 25 mg of Evobrutinib which was enough medication for the administration of 6 tablets per day (3 in the morning and 3 in the evening) for 8 days. At each trial visit, a participant was given treatment kits containing the number of tablets needed up to the next planned trial visit. Number of kits dispensed was the same as before the switch of dose. After the switch, participants received 75 mg of Evobrutinib BID (twice a day) for the remainder of the OLE.

Exposure

Exposure time in weeks during the OLE will be calculated according to the following formula:

exposure (weeks) = (date of last dose during OLE period - date of first dose during OLE period + 1)/7

If the end date of the last dose is missing, then the date of last dose will be replaced by the last visit date. If a participant is lost to follow up and hasn't performed the EOT visit, then end of study date will be considered as the end of treatment date.

Exposure time will be presented by summary statistics during the OLE period and according to the categories \leq 1 week, > 1 to 12 weeks, > 12 to 24 weeks, > 24 to 36 weeks, > 36 to 48 weeks, > 48 to 60 weeks, > 60 to 72 weeks, > 72 to 84 weeks, > 84 to 96 weeks, > 96 to 108 weeks, > 108 to 120 weeks, > 120 to 132 weeks, > 132 to 144 weeks > 144 to 156 weeks, > 156 to 168 weeks, > 168 to 180 weeks, > 180 to 192 weeks, > 192 to 216 weeks, > 216 to 240 weeks, > 240 to 264 weeks, > 264 to 288 weeks, > 288 to 312 weeks, > 312 weeks. For this analysis the SAF-OLE analysis set will be used. Tables about exposure time before or after the switch during the OLE period will be provided, the day of switch will be considered in the period after the switch. For tables about exposure time after the switch, the SAF-SWOLE analysis set will be used.

The cumulative actual dose (mg) per participant is the number of tablets taken during the OLE period, multiplied by 25 mg (dosage of 1 tablet). The number of tablets ingested will be deduced from the "M2951 Box Number (BATCH3)" electronic case report form (eCRF) page. Descriptive statistics for cumulative actual dose will be presented during OLE period using the SAF-OLE analysis set. Descriptive statistics for cumulative actual dose received before and after the switch during the OLE period will be also provided. Descriptive statistics after the switch will be restricted to SAF-SWOLE Analysis Set.

Compliance

Compliance with treatment during OLE period =
$$100*(\frac{(N_{1bs})}{3*N_{2bs}} + \frac{(N_{1as})}{6*N_{2as}})$$

where

- N_{1bs} = number of tablets given minus number of tablets returned before dose switch,
- - N_{2bs} = number of days between treatment start and switch visit (or treatment termination visit if participant discontinued before the switch),
- - N_{1as} = number of tablets given minus number of tablets returned after dose switch,
- $-N_{2as}$ = number of days between switch visit and treatment termination visit. For participants who are lost to follow-up the end of study visit date will be used.

Compliance with treatment before the switch during OLE period is defined as $100^*(\frac{(N_{1bs})}{3*N_{2bs}})$

Compliance with treatment after the switch during OLE period is defined as $100*(\frac{(N_{1as})}{6*N_{2as}})$

If the subject didn't switch the dose, $\frac{(N_{1as})}{6*N_{2as}}$ is set to 0. If a kit is received by the participant but no information about the number of tablets returned is available because of lost to follow-up, the kit is not considered in the calculation of compliance.

Compliance with treatment will be presented by summary statistics during the OLE period and according to the categories < 60%, $\ge 60\%$ to < 80%, $\ge 80\%$ to < 90%, $\ge 90\%$ to < 110%, $\ge 100\%$. For this analysis the SAF-OLE analysis set will be used. Tables about compliance before or after the switch during OLE period will be also provided. Tables after the switch will be restricted to SAF-SWOLE Analysis Set.

The following listings will be provided:

- listing of Evobrutinib start/end dates of the single administration with number of ingested tablets (from EXPOSUREDT3 eCRF page), for the study drug administration during the OLE period.
- listing with exposure time, cumulative dose, and compliance during the OLE period.

16 Efficacy Evaluation

All efficacy analyses will be based on the mITT and mITT-OLE analysis sets, as specified in below sections. All analyses are descriptive, there is no hypothesis testing.

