Upon Principal Investigator request, a participant in this circumstance at Week 96 of the OLE Period may still be able to continue into the 240-week extension of the OLE with approval from Merck/EMD Serono, on a case-by-case basis, provided that the treatment gap would not exceed 90 days from the last evobrutinib dose received in the first 96 weeks of OLE Period (OLE Week 96 Visit) to the first evobrutinib dose received in the 240-week extension of the OLE Period.

Participants with a treatment gap should attend the study site upon resumption of treatment. Unless otherwise clinically indicated, only the following procedures should be performed at this visit:

- Review concomitant medications and AEs;
- Allow the Investigator to ensure that the participant remains eligible for the study (see Section 5.4), including urine pregnancy test if applicable;
- Dispensing evobrutinib;
- EDSS (only if the treatment gap is ≥ 4 weeks).

See Section 6.4.2.1 for details of whether alternate treatment for RMS should be administered during a treatment gap that results from pending regulatory approval for the extension of the OLE Period.

Participants with a treatment gap following Week 96 of the OLE Period who restart study drug should attend any scheduled telephone visits and the Week 108 Visit (Visit 12) as scheduled.

Once the long-term follow-up study is open for enrollment in their country (i.e., once the Sponsor, upon agreement with Health Authorities/Ethics Committees, will have notified sites), participants in the OLE period will have the option to transition into the long-term follow-up study under a new protocol within 30 days of Sponsor notification, allowing continued access to study treatment (refer to Sections 7.7.1 and 7.1.8).

7.1.6.1 **Telephone Visits**

After Week 96 of the OLE Period, on-site visits become less frequent. During this period, regular Telephone Visits with participants are scheduled, as per Table 3.

During the Telephone Visits, the following should be discussed with the participant:

- Any AEs or SAEs that may have occurred since the last on-site visit/phone call;
- Any changes in concomitant medications that may have occurred since the last on-site visit/phone call;
- Occurrence of MS relapses since the last on-site visit/phone call;
- Overall well-being;
- Pregnancy, if applicable;
- Occurrence of other notable medical events (e.g., surgeries, injuries, laboratory tests performed outside the study);

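### SAP 15 counts the Week 96 treatment gap as exposure and in the compliance denominator; for participants lost to follow-up, the two parts of the compliance ratio cover different periods

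*SAP*

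**What the plan says.** **Exposure (SAP 15).** OLE exposure in weeks is "date of last dose during OLE period - date of first dose during OLE period + 1", divided by 7. Nothing is subtracted for interruptions. Two rules supply a missing end. If the last-dose date is missing, "then the date of last dose will be replaced by the last visit date". If a participant is lost to follow-up without an end-of-treatment visit, "then end of study date will be considered as the end of treatment date". The SAP does not say which rule applies when a participant meets both conditions.

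**Compliance (SAP 15).** After the dose switch, compliance is 100 × N1as / (6 × N2as). N1as is tablets given minus tablets returned, and N2as is the "number of days between switch visit and treatment termination visit". For participants lost to follow-up, N2as instead runs to the end-of-study visit date. Where a kit has no return count because of loss to follow-up, "the kit is not considered in the calculation of compliance".

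**The gap.** Protocol 7.1.6 lets a participant continue past OLE Week 96 after an administrative delay if "the treatment gap would not exceed 90 days from the last evobrutinib dose received in the first 96 weeks of OLE Period" to the first dose of the extension. The SAP is aware of this. Section 12.1 tabulates the "Number of subjects who entered a gap period at OLE Week 96", and Section 17.1 treats adverse events starting in the gap as treatment-emergent and flags them. Section 15 has no rule for the gap.

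**The concern.** The exposure tables are meant to show how long participants were treated, and the compliance tables how closely they followed the regimen. As written, both also reflect time when no study drug could be taken. A maximum gap lengthens exposure and lowers after-switch compliance whatever the participant did. Gap time may also be time on another MS drug: Protocol 6.4.2.1 allows alternate RMS treatment during the gap and forbids its use alongside study drug.

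For participants lost to follow-up, the compliance problem is one of construction. Tablets from kits with no return count are left out, but N2as still runs to the end-of-study visit. The numerator stops at the last accountable kit and the denominator does not.

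At stake are the exposure categories and the compliance display bands, which have cut-points at 60%, 80% and 90%.

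**Working it through.** The documents give no exposure or compliance result, so there is no figure to reproduce. The check applies the SAP 15 formulas to a participant who takes every tablet available.

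**Inputs from the documents**
- Maximum gap: 90 days from last dose to next dose (Protocol 7.1.6), so at most 90 − 1 = 89 dose-free days, and 89 / 7 = 12.7 weeks.
- OLE Week 96 is Day 672 and Week 108 is Day 756 (Protocol Tables 2 and 3).
- Exposure bands are 12 weeks wide between Weeks 12 and 192, then 24 weeks wide up to Week 312 (SAP 15).
- On-site visits are 12 weeks apart from Week 96 to Week 192 and 24 weeks apart after that (Protocol Table 3).

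**Assumptions:** the week of dose switch, the week of stopping, and the lag from last accountable visit to end-of-study date. The documents give none of these for any participant.

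**1. Exposure with a maximum gap**

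| Stop week | SAP exposure (weeks) | Net of 89 days (weeks) |
|---|---|---|
| 120 | 120 | 107.3 |
| 144 | 144 | 131.3 |
| 240 | 240 | 227.3 |
| 336 | 336 | 323.3 |

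Because 12.7 weeks exceeds a 12-week band, a maximum gap places a participant at least one category too high for any stop up to Week 192. In the wider later bands it may not: 240 and 227.3 both fall in >216 to 240 weeks, and 336 and 323.3 both exceed 312.

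**2. After-switch compliance with a maximum gap**

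Let D = 7 × (stop week − switch week). With full intake, N1as = 6 × (D − 89), so compliance = 100 × (D − 89) / D.

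| Switch week | Stop week | D (days) | Compliance |
|---|---|---|---|
| 48 | 120 | 504 | 415/504 = 82.3% |
| 48 | 144 | 672 | 583/672 = 86.8% |
| 84 | 144 | 420 | 331/420 = 78.8% |
| 48 | 336 | 2016 | 1927/2016 = 95.6% |

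The value is below 80% when 89 / D > 0.20, that is D < 445 days (63.6 weeks). It is below 90% when D < 890 days (127 weeks). A maximum gap ends on Day 672 + 90 = 762, so a participant who restarts and still has D < 445 must have switched after Day 762 − 445 = 317 (about Week 45). With the gap days removed, every row is 100%.

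**3. Lost to follow-up, no gap, switch at Week 48**

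With full intake to the last accountable visit and later kits excluded, compliance = 100 × D / (D + 7 × lag in weeks), where D runs from the switch to that visit.

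| Last accountable visit | Lag 4 weeks | Lag 12 weeks | Lag 24 weeks |
|---|---|---|---|
| Week 144 (D = 672) | 96.0% | 88.9% | 80.0% |
| Week 216 (D = 1176) | 97.7% | 93.3% | 87.5% |

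If the end-of-study rule sets the end of treatment, exposure lengthens by the same 4, 12 or 24 weeks. The 24-week lag equals one visit interval after Week 192; before that an interval is 12 weeks. Ending both parts of the ratio at the last accountable visit returns 100%.

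**The case against.** First-to-last-dose span is a legitimate duration measure, and much is already shown elsewhere: tablet-based cumulative dose, which the gap does not inflate; a listing of administration dates; the count of gap entrants; and the flagged adverse events. This stands, and it is why net exposure should sit beside the calendar span rather than replace it. It does not correct the compliance denominator.

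Three stronger readings are tempting, and the documents do not support them.

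- **That a fully adherent participant breaches the protocol's 80% limit.** Protocol 6.8 defines insufficient compliance against the required number of scheduled doses. An approved gap has none. What changes is an SAP display band.
- **That a Week 48 switch, a 90-day gap and a Week 108 stop give (420 − 90)/420 = 78.6%.** The gap would end on Day 762, after Week 108 (Day 756). Only 84 days lie between Week 96 and Week 108, which gives 336/420 = 80.0%.
- **That days after a lost participant's last visit are drug-free.** They are unaccounted for. These participants left with dispensed tablets, and some may have taken them. Telephone Visits, about 8 weeks apart after Week 192, may also reveal a loss well before 24 weeks.

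The kit sentence does not itself say what happens to that kit's days. The mismatch follows from reading it with the N2as rule, which does extend to the end-of-study visit.

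Finally, the understatement applies to the separate before- and after-switch tables. The overall OLE formula adds the two ratios, so a full complier who switched scores about 200%. That is a distinct error, best corrected in the same edit.

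**Conclusion.** The point holds and is minor. SAP 15 includes up to 89 dose-free days (12.7 weeks) in exposure and in the compliance denominator for anyone with a maximum Week 96 gap, and it mismatches the two parts of the compliance ratio for participants lost to follow-up. This is a fault in the stated rules, not just missing detail.

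Under the assumed switch and stop weeks, a full complier with a maximum gap shows 78.8% to 95.6% after the switch. A value below 80% needs a switch-to-stop span under 445 days. Shorter gaps have smaller effects, and the number affected is not given.

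Only the exposure tables and the before- and after-switch compliance tables are touched. SAP 16 plans no hypothesis testing, SAP 10.1 excludes nobody from an analysis set for protocol deviations, and the exposure-adjusted incidence rates in SAP 17.1.1.2 define their own person-time.

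**What to change.** Amend SAP 15 in four places:

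1. Report OLE exposure net of the documented Week 96 gap, beside the calendar span.
2. Subtract gap days from N2as, or from N2bs for a participant who had not yet switched.
3. For participants lost to follow-up, end both numerator and denominator at the last visit with tablet accountability.
4. State which end date prevails when a participant has a missing last-dose date and is also lost without an end-of-treatment visit, and whether a recorded last-dose date overrides both.

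The cost is a few lines of text and a small programming change. Administration start and end dates are already due to be listed under SAP 15, and gap entrants are already identified under SAP 12.1, so no new data are needed.

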11.1 Treatment groups and Investigational Medical Product (IMP)

Treatment groups are defined according to initial actual treatment received as placebo, Evobrutinib 25 mg QD, Evobrutinib 75 mg QD, Evobrutinib 75 mg BID, and Tecfidera. All participants who choose to continue the OLE period entered on the 75 mg once daily dose and have switched to the 75 mg twice daily dose following protocol amendment V5 dated 21 November 2018. Unless otherwise indicated, all analyses will be presented separately for the 5 initial treatment groups plus combined across treatment groups (i.e., "Total"). The IMP during the OLE phase is Evobrutinib.

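### Overall OLE compliance adds the before-switch and after-switch ratios instead of pooling them, so a switcher with compliance c in both periods is reported as 2c

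*SAP*

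**What the plan says.** SAP Section 15 (Compliance) gives overall OLE compliance as "100*(\frac{(N_{1bs})}{3*N_{2bs}} + \frac{(N_{1as})}{6*N_{2as", with the brackets then closed. N1bs and N1as are tablets given minus tablets returned before and after the switch. N2bs and N2as are the days in each of those two periods.

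The same section then defines the period values from the same two terms:

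- "Compliance with treatment before the switch during OLE period is defined as" 100 × N1bs / (3 × N2bs).
- "Compliance with treatment after the switch during OLE period is defined as" 100 × N1as / (6 × N2as).

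For participants who stayed on once-daily dosing: "If the subject didn't switch the dose, $\frac{(N_{1as})}{6*N_{2as}}$ is set to 0".

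The overall value is summarised on SAF-OLE with summary statistics and categories cut at 60, 80, 90 and 110%. It also appears in a "listing with exposure time, cumulative dose, and compliance during the OLE period". Separately, "Tables about compliance before or after the switch during OLE period will be also provided". SAP Section 11.1 says that participants who continued into the OLE "entered on the 75 mg once daily dose and have switched to the 75 mg twice daily dose".

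**The concern.** Compliance over two consecutive periods should be total tablets taken over total tablets due. The SAP instead adds two ratios that each run from 0 to 1, with no weights and no division. The result is on a 0 to 200% scale for switchers and a 0 to 100% scale for everyone else, and both groups enter the same summary. The sum also ignores how long each period lasted, so a short once-daily period counts as much as several years of twice-daily dosing.

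At stake is whether the overall compliance table can be read at all. Protocol Section 6.8 defines insufficient compliance as less than 80% of scheduled doses. The overall table would place many participants below that limit in the acceptable range or above it. Section 11.1 makes switching the expected case, although the documents give no count of switchers.

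**Working it through.** **Inputs.** SAP Section 15 gives 24-tablet kits lasting 8 days before the switch (24 / 8 = 3 tablets a day) and 48-tablet kits lasting 8 days after it (48 / 8 = 6 a day). So 3 × N2bs and 6 × N2as are the tablets due in each period. The documents state no compliance result, so there is no figure to reproduce. All day counts below are assumptions.

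**Formulas.** Let c1 and c2 be true compliance before and after the switch, and d1 and d2 the days.

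- SAP value = 100 × (c1 + c2).
- Pooled value = 100 × (3·d1·c1 + 6·d2·c2) / (3·d1 + 6·d2) = 100 × (w1·c1 + w2·c2), where w1 = 3·d1 / (3·d1 + 6·d2) and w2 = 1 − w1.
- SAP minus pooled = 100 × (w2·c1 + w1·c2). This is a weighted average of the two compliances, so it is never below the lower of them.

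**Full compliance, 336 days in each period.** Tablets due are 3 × 336 = 1008 and 6 × 336 = 2016. SAP: 100 × (1008/1008 + 2016/2016) = 200%. Pooled: 100 × 3024/3024 = 100%.

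**Equal compliance in both periods, any split of days.**

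| True c | SAP value | Pooled |
|---|---|---|
| 100% | 200% | 100% |
| 95% | 190% | 95% |
| 79% | 158% | 79% |
| 50% | 100% | 50% |
| 40% | 80% | 40% |

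The cut-points 60, 80, 90 and 110% therefore correspond to true values of 30, 40, 45 and 55%. Because the SAP value is a plain sum, any switcher with at least 40% in each period shows 80% or more, and any with at least 55% in each shows 110% or more.

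**Unequal compliance.** Assumed once-daily/twice-daily days are 168/336, 350/1500 and 168/2000, giving w1 = 504/2520 = 0.200, 1050/10050 = 0.104 and 504/12504 = 0.040.

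| Before / after | SAP value | Pooled, 168/336 | Pooled, 350/1500 | Pooled, 168/2000 |
|---|---|---|---|---|
| 95% / 70% | 165% | 75.0% | 72.6% | 71.0% |
| 90% / 40% | 130% | 50.0% | 45.2% | 42.0% |
| 10% / 60% | 70% | 50.0% | 54.8% | 58.0% |

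The last row is a milder case, with an excess of 20.0, 15.2 and 12.0 points.

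**Non-switcher.** The second term is 0, so the SAP value is 100 × c1, which is correct.

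**The case against.** **A weight or a factor of one half may have been lost when the PDF was read.** This does not stand. The list of symbols under the formula defines nothing else, the two period definitions reuse the same terms whole, and setting the second term to 0 for non-switchers fits only a plain sum.

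**The output is descriptive, and values near 200% would be noticed.** The first part is true and limits the consequence: the period tables are on the correct scale, and no efficacy or safety analysis uses the overall value. The second part helps less. Combined values of 80 to 110% from participants at 40 to 55% would not look odd, and a correction made only in the programs would leave the output at odds with the SAP.

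**Not everyone need be a switcher.** Protocol Sections 5.1, 5.5 and 6.2 allow direct entry to the OLE on twice-daily dosing, and SAP Section 11.2 limits the switch to participants still ongoing. For the Final Analysis, SAP Section 11.1 says that all entered once daily, so direct entrants should be an empty group. What stands is that the number of switchers is unknown, and that the replacement formula is safer if its terms are defined by dose period.

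**Conclusion.** The formula is wrong as written. It doubles reported compliance when compliance is equal in both periods. Otherwise it reports the sum of the two percentages, which exceeds the pooled value by at least the lower of them. This is exact algebra and needs no assumption about period lengths; only the unequal-compliance examples rest on assumed days. How many participants are affected cannot be stated from the documents. The damage is limited to the overall SAF-OLE compliance statistics, categories and listing. It should be fixed before those are produced.

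Two smaller matters in the same section are separate from this conclusion:

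- The category labels read "\ge 90\%$ to < 110%, $\ge 100" per cent, so the last two overlap. This may be a typing slip or a misread of 110%, and needs only a check against the source.
- For participants lost to follow-up, kits without return data are left out, yet N2as runs to the end of study visit date. If the days covered by those kits stay in the denominator, tablets and days do not match. For example, a participant who took every tablet, with 84 of 700 twice-daily days covered by dropped kits (assumed), would show (700 − 84) / 700 = 88.0%. The text can also be read as dropping those days, so this is a request for clarification.

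**What to change.** Replace the overall formula in SAP Section 15 with

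100 × (N1bs + N1as) / (3 × N2bs + 6 × N2as),

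setting N1as = N2as = 0 for participants who did not switch. Defining the terms by dose period (once-daily tablets and days, twice-daily tablets and days, each 0 if that period did not occur) would also cover anyone who entered directly on twice-daily dosing. The pooled ratio returns c when compliance is c in both periods, whatever their lengths, and leaves non-switchers unchanged. It uses only quantities already defined, so the cost is one formula and a small programming change.

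As separate minor edits, check the label of the top category, and state how the dropped-kit rule and the end date for N2as work together so that tablets and days cover the same interval. The second may change a stated rule.
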